# 2. HYPOTHESIS AND OBJECTIVES

Aims

Primary aims

- 1. Explore primary care professionals' (PCPs) perspectives and challenges in management of gout and assess whether novel gout action plan addresses the challenges.
- 2. Explore patients' understanding of gout, experiences and challenges of managing gout and medications, and assess whether they are willing to use novel gout action plan.

Secondary aims:

- 1. Assess the feasibility and acceptability of gout action plan in a pilot open label randomized controlled trial (RCT).
- 2. Assess preliminary effectiveness of gout action plan in reducing frequency of gout exacerbation, improving gout control and quality of life.

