#### **Randomization**

Patients will be randomly assigned in a 1:1 ratio to either control or intervention arm in an open-label fashion, using computer-generated random numbers for randomization of subjects. The randomized sequence will be written and kept in an opaque sealed envelope and labelled with a serial number. When patients consent to participate in the study, the team will open the opaque sealed envelope and allocated them to the study arms accordingly. It is impossible to blind the patients and research team members to the patient allocation in view of the nature of the intervention.

Upon recruitment and after patient consented, basic patient demographics and data on their gout duration, comorbidities and medications will be collected using the attached data collection form. They will be asked to recall and self-report frequency of gout flares for the past 6 months prior to recruitment. They will also need to fill up an EQ-5D-5L questionnaire on health-related quality of life which takes approximately 5 minutes to fill it up. They will also be sent for laboratory for blood test to test for uric acid level. Blood will be taken from arm using a syringe and needle, during recruitment and at a 6-month visit, for participants in both intervention and control groups. About 3ml of blood will be taken each time. In total, there will be about 6ml taken over a period of 6 months. The Institutional Review Board waiver under Section 37(3) of the Human Biomedical Research Act

2015 ("HBRA") for the removal of human biological materials is not required. This is because we will collect samples from adults with mental capacity to personally give consent for this research study.

For those patients who are assigned into the intervention arm, they will be sent to care manager to explain on the gout action plan and its details.

Study participants will be followed up for 24 weeks after enrolment. At 24 weeks, they will be asked on their frequency on gout flares after the recruitment and to fill up the EQ-5D-5L questionnaire together. They will also be sent to laboratory for blood test on uric acid level. The follow up survey will be conducted by phone call or questionnaire at a convenient time for them or during the clinic visit.

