#### 2) Difficulties during interviews

- As patient participants are recruited on the day of their visit to the clinic, not all will be free for face-to-face interview on the same day. Similarly, not all HCPs will be free for face-to-face interview on the same day as recruitment. Some participants may prefer to have interview done on a different day.

Alternative approach: the research team may offer the option of a face-to-face interview to the participants depending on his or her availability.

3) Lost to follow up

- In open label RCT for 24 weeks, patients might not return for follow up during the subsequent visit. Proposed measures will include message reminders to patients on their follow up visit.

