# 8. SAMPLE SIZE AND STATISTICAL METHODS

### 8.1. Determination of Sample Size

For qualitative part, sample size calculation is not applicable. Prototype of gout action plan will be refined until saturation is reached. Hennink  showed that 9-17 interviews or 4-8 focus group discussion reached saturation for studies with relatively homogenous study populations and narrowly defined objectives. Therefore, for this study, we aim to recruit 10-15 participants from each group.

For pilot RCT, based on sample size rule of thumb for pilot study, Browne  cites to 'use at least 30 subjects or greater to estimate a parameter', whereas Whitehead  suggests that pilot trial sample size to be 25 per treatment arm for small effect size of 0.2 for a main trial designed with 90% power and two-sided 5% significance. With a 6-months follow up visit, assuming a potential 30% attrition rate, the final sample size after buffering for drop out will be 36 per arm (n=72). The sampling method will be convenience sampling.

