#### Quantitative data:

Descriptive statistics will be generated for the baseline characteristics of the study participants, and frequencies and percentages will be presented for categorical variables while mean and standard deviation will be presented for continuous variables.

To assess effectiveness of gout action plan, the continuous outcome between the two groups will be compared using independent t-test. When outcomes are categorized into binary outcomes, Chi-square test will be performed. The baseline outcomes will also be assessed with demographic using either Chi-square test or Fisher's Exact test for categorical variables, and independent t-test or ANOVA for continuous variables to ensure both groups are comparable. Multivariate linear regression model will be performed with each outcome below and the following covariates to determine effectiveness of the intervention: intervention (gout action plan), baseline outcome and any demographic factors with a p-value of less than 0.1 in the bivariate analysis. All analyses will be performed using SPSS software version 29.0. A p-value of less than 0.05 is considered to be statistically significant.

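### Does an open-ended flare count at a loosely timed 24-week survey, analysed by linear regression without exposure time, bias the comparison between arms?

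*Protocol*

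**What the plan says.** The effectiveness aim in Protocol Section 2 is secondary and names flares first: "Assess preliminary effectiveness of gout action plan in reducing frequency of gout exacerbation, improving gout control and quality of life".

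Section 5, Part 2, gives the action plan for 24 weeks, and the Randomization text follows every participant for 24 weeks from enrolment. The outcome question comes next: "At 24 weeks, they will be asked on their frequency on gout flares after the recruitment". On how contact is made: "The follow up survey will be conducted by phone call or questionnaire at a convenient time for them or during the clinic visit".

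Two other places use months. On the uric acid sample: "Blood will be taken from arm using a syringe and needle, during recruitment and at a 6-month visit". In Section 8.1: "With a 6-months follow up visit, assuming a potential 30% attrition rate". The baseline flare count also covers months: "They will be asked to recall and self-report frequency of gout flares for the past 6 months prior to recruitment".

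Section 5 also foresees losses, in its list of difficulties: "In open label RCT for 24 weeks, patients might not return for follow up during the subsequent visit". It answers with message reminders.

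Section 8.2 sets the analysis: "Multivariate linear regression model will be performed with each outcome below and the following covariates". The covariates are the intervention, the baseline value and demographic factors selected at p<0.1. No list of outcomes follows, so it is inferred from the aim in Section 2 that flares are among them. The same section also provides a t-test for continuous outcomes and a chi-square test where outcomes are made binary.

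**The concern.** A flare count grows with the time over which it is taken. Here the count starts at recruitment and, read literally, ends on the day the patient is asked. With no tolerance around week 24 and flexible contact, a patient reached late reports more than 24 weeks of flares. The planned model has no exposure term to allow for this.

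The trial is open label, and only the intervention arm is sent to a care manager. One can therefore imagine one arm being reached sooner than the other. The extra weeks in the later arm would then enter the between-arm difference, and linear regression on baseline and demographics could not remove them. A patient asked only about flares since recruitment could not later supply a 24-week count. The switching between 24 weeks and six months adds to the impression that the window is not settled.

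**Working it through.** **1. The Protocol's own figure.** Section 8.1 takes 25 per arm and 30% attrition: 25 / (1 − 0.30) = 35.71, rounded up to 36 per arm, 72 in total. This reproduces and does not depend on the follow-up label.

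**2. The two labels.** 24 × 7 = 168 days. Six months is 365.25 / 2 = 182.6 days. The difference is 14.6 days, and 182.6 / 168 = 1.087. At a constant flare rate the longer window yields 8.7% more flares. Section 5 schedules the six-month sample for both arms, so the excess is common to both.

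**3. Effect of a late survey on one arm.** The expected count is multiplied by (24 + delay) / 24: 1.083 for 2 weeks, 1.167 for 4 weeks and 1.333 for 8 weeks. If only one arm is late, the spurious difference is mean × delay / 24. For a mean of 1 to 2 flares per 24 weeks that is 0.08 to 0.17 flares at 2 weeks and 0.17 to 0.33 at 4 weeks.

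**4. Type I error of the planned model.** The Protocol gives no flare rates, so these are assumptions: mean 1 to 2 flares per 24 weeks, gamma-Poisson counts with dispersion 0.7 to 1.5, 25 analysed per arm, a patient-level rate shared by baseline and follow-up, baseline counted over 182.6 days, and no true effect. There were 3,000 simulated trials per cell; the Monte Carlo standard error at 5% is √(0.05 × 0.95 / 3000), about 0.4 points. Entries are the rejection rate of the baseline-adjusted linear model, with the size of the spurious difference in flares in brackets.

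| Mean, dispersion | No gap | 0–8 weeks late, both arms alike | One arm 2 weeks later | One arm 4 weeks later |
|---|---|---|---|---|
| 1, 1 | 4.2% | 5.1% | 5.1% (0.074) | 7.1% (0.159) |
| 1.5, 1 | 5.0% | 4.9% | 6.1% (0.112) | 7.3% (0.233) |
| 1.5, 1.5 | 5.0% | 4.8% | 4.9% (0.113) | 8.1% (0.241) |
| 2, 0.7 | 5.2% | 5.1% | 5.8% (0.152) | 8.9% (0.333) |

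In the two-week column, two cells cannot be told from 5% and the other two lie 0.8 and 1.1 points above it.

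**5. Cross-check with the unadjusted t-test** (means 1 to 3, dispersion 1, 20,000 trials per cell). Timing alike in both arms: 4.6% to 4.9%. One arm later by 2 weeks: 5.3% to 5.4%. By 4 weeks: 6.4% to 7.0%. By 8 weeks: 10.5% to 12.9%.

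**6. What a count model would gain.** At a rate ratio of 0.5 with no gap, taking the four settings in table order, power is 36.8%, 50.8%, 44.7% and 65.1% for the linear model. For quasi-Poisson regression with a log-time offset it is 37.0%, 51.7%, 48.0% and 65.3%. The gains are 0.2, 0.9, 3.3 and 0.2 points. Size with no gap is 3.9% to 5.8% for quasi-Poisson and 4.2% to 5.2% for linear, so neither has an advantage there.

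**7. The baseline window.** Six months before against 24 weeks after would inflate the baseline side of a descriptive before-after contrast by 8.7%. In the planned analysis baseline is a covariate measured before allocation over the same period in both arms, so it does not bias the between-arm estimate.

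**The case for a change.** The best case for acting is that the recall question has to be right before data are collected. An analysis plan could add an offset, but it could not recover a fixed 24-week count from patients asked only about flares since recruitment. The labels also conflict inside one section, which places the uric acid test both at 24 weeks and at six months. Under an assumed four-week gap, stopping the count at day 168 returns the same linear model to 4.7% to 5.7%, at the cost of a reworded question and a date field.

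Some of this stands. The labels are inconsistent, no tolerance is stated, and the count has no explicit cut-off. The arithmetic for a gap between arms is also correct. But the case needs the gap, and the Protocol does not supply one:

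- An end point is set. The question is put at 24 weeks, after a stated 24 weeks of follow-up. The sentence on convenience comes after that and reads naturally as the hour and mode of contact, not as leave to delay.
- The passage on patients not returning describes loss to follow-up, which means missing data. It does not describe late surveys.
- Survey tolerances and date fields usually sit in the data collection form or the analysis plan. The form is attached to the Protocol but not reproduced, so one cannot say that the date goes unrecorded.
- An offset would do almost nothing if patients are asked at 24 weeks, because every surveyed patient then has about the same exposure. The Protocol describes no follow-up contact between baseline and 24 weeks at which a shorter exposure could be recorded.

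**Conclusion.** No change is needed. If the survey is held at 24 weeks in both arms, as the Protocol says, or runs late to the same extent in both, the planned comparison of flares keeps its nominal error rate within simulation error. The only timing discrepancy in the text is about two weeks and common to both arms. Even placed wholly on one arm it moves the type I error to at most about 6%, in a pilot where effectiveness is a secondary and preliminary aim. Larger distortions need a mean gap of four weeks or more between arms, which the documents neither show nor imply. Replacing linear regression would be a matter of preference, with a gain of about 0 to 3 points of power.

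These figures rest on assumed flare rates and dispersion and on 25 analysed patients per arm. The conclusion that equal timing leaves the comparison unbiased does not depend on those rates. What is left is a clerical slip in the follow-up label and a recall period that staff and analysts would sensibly take as 24 weeks. If survey dates turned out to differ by arm, an analysis with a log-time offset would be a reasonable sensitivity check, and nothing in the Protocol prevents it.

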#### Participant withdrawal

Participants may choose to withdraw from the study at any time without providing an explanation and this will not result in any punitive consequences.

#### Potential difficulties and limitations and alternative approaches to achieve the aim

1) Recruitment

- In the event of difficulty recruiting adequate number of patients, proposed measures will include

- 1. Email reminders and message reminders to staffs in clinic to look for patients with gout
- 2. Obtaining prior knowledge of a potential participant's medical appointment so that the physician of that day can be reminded about the potential participant's arrival.
- In the event of difficulty recruiting adequate number of physicians
  - 1. Making use of primary care message groups and networks to reach out to potential HCPs participants
  - 2. Speaking to family medicine department heads or private general practice group heads to help disseminate the need for participants

#### 2) Difficulties during interviews

- As patient participants are recruited on the day of their visit to the clinic, not all will be free for face-to-face interview on the same day. Similarly, not all HCPs will be free for face-to-face interview on the same day as recruitment. Some participants may prefer to have interview done on a different day.

Alternative approach: the research team may offer the option of a face-to-face interview to the participants depending on his or her availability.

3) Lost to follow up

- In open label RCT for 24 weeks, patients might not return for follow up during the subsequent visit. Proposed measures will include message reminders to patients on their follow up visit.

# 6. SAFETY MEASUREMENTS

#### 6.1. Definitions

Serious adverse event (SAE) in relation to human biomedical research, means any untoward medical occurrence as a result of any human biomedical research which:

- results in or contributes to death
- is life-threatening
- requires in-patient hospitalisation or prolongation of existing hospitalisation
- results in or contributes to persistent or significant disability/incapacity or
- results in or contributes to a congenital anomaly/birth defect

• results in such other events as may be prescribed

Adverse event (AE) in relation to human biomedical research means any untoward medical occurrence as a result of any human biomedical research which is NOT serious. Adverse event can be any unfavourable and unintended sign (including an abnormal laboratory finding), symptom, or disease possibly/ probably/ definitely associated with the participant in the human biomedical research.

#### 6.2. Collecting, Recording and Reporting of Serious Adverse Events (SAEs) to CIRB

The reporting requirements will be in accordance to the reporting requirements published on CIRB website at the time when the event took place.

Only related SAEs (definitely/ probably/ possibly) will be reported to CIRB. Related means there is a reasonable possibility that the event may have been caused by participation in the research.

The investigator is responsible for informing CIRB after first knowledge that the case qualifies for reporting. Follow-up information will be actively sought and submitted as it becomes available.

Related AEs will not be reported to CIRB. However, the investigator is responsible to keep record of such AEs cases at the Study Site File.

#### 6.3. Safety Monitoring Plan

After each interview, the interviewer will transfer the audio-recording to a password-protected corporate laptop and erase it from the audio-recorder. The soft copy research data will be stored in institution issued PC and hard copy will be kept under lock and key for 6 years before they are deleted. They will always be password protected, and data will not be transferred using thumb drive of other unsecured means.

#### 6.4. Complaint Handling

All complaints will be reviewed by the study team and escalate to clinic director/ supervisor of Research department.

# 7. DATA ANALYSIS

#### 7.1. Data Quality Assurance

Study data will be checked and validated by data management executive in Department of Research to ensure that the data obtained from this research is accurate, complete and reliable.

#### 7.2. Data Entry and Storage

Information from the hard copy (data collection forms, questionnaires and consent forms) will be transcribed to a Microsoft Excel document with password protection. The hard copy documents will be kept in a research folder, stored under lock and key in the polyclinic research room at Pasir Ris polyclinic. The folder will not be taken out of the clinic.

After each interview, the interviewer will transfer the audio-recording to a password-protected corporate laptop and erase it from the audio-recorder. The audio recording will be transcribed verbatim using the research department's transcribing software or transcription platforms (such as transcribe.gov.sg or Note Buddy) or engagement of transcriptionist. All participant identifiers will be removed from the transcript to ensure confidentiality. All transcripts will be checked by interviewer for accuracy. De-identified data will be used for analysis. All the audio files and transcriptions of the recordings will have password encryption and stored in the same password-protected corporate laptop in workplace. Only study members will have access to the password. Information from the data collection form will be transcribed to excel document (with password encryption) in a password-protected corporate laptop in workplace. There will be no USB or removal device used for data storage. The physical consent forms and the electronic data will be kept for 6 years post completion of study. The physical consent forms will be stored in a secure physical archive and the electronic data in an electronic archive. Only the principal investigator and co-investigators will have access to the archives.

# 8. SAMPLE SIZE AND STATISTICAL METHODS

### 8.1. Determination of Sample Size

For qualitative part, sample size calculation is not applicable. Prototype of gout action plan will be refined until saturation is reached. Hennink  showed that 9-17 interviews or 4-8 focus group discussion reached saturation for studies with relatively homogenous study populations and narrowly defined objectives. Therefore, for this study, we aim to recruit 10-15 participants from each group.

For pilot RCT, based on sample size rule of thumb for pilot study, Browne  cites to 'use at least 30 subjects or greater to estimate a parameter', whereas Whitehead  suggests that pilot trial sample size to be 25 per treatment arm for small effect size of 0.2 for a main trial designed with 90% power and two-sided 5% significance. With a 6-months follow up visit, assuming a potential 30% attrition rate, the final sample size after buffering for drop out will be 36 per arm (n=72). The sampling method will be convenience sampling.

## 8.2. Statistical and Analytical Plans

Qualitative and quantitative data will be analyzed separately.

#### Qualitative data:

Audio recordings of the interviews will be transcribed using the research department's transcribing software or transcription platforms (such as transcribe.gov.sg or Note Buddy) or engagement of transcriptionist. All personal identifiable information will be removed. The transcripts will be sent to the study team through secured email and reviewed for accuracy and completeness prior to data analysis. In the event of significant errors being found, they will be sent back to transcribers or transcribing platforms or transcribing software for amendments. The transcripts will be analyzed to understand the views of healthcare providers and patients on gout action plan. Thematic analysis will be performed by at least 2 study team members after familiarizing with the data. Using grounded theory approach, codes and the respective data extracts will be categorized into broader themes and subthemes to form a coding framework which will be refined iteratively as data from the first 2-3 participants are analyzed. Identification of themes, needs and information will help in creation of prototype of gout action plan. In the event of discrepancies in the coding framework among the study team members, this will be resolved through consensus and if necessary, by engaging another study team member to analyze the data to reach an eventual coding framework.

Computer-assisted qualitative data analysis software Nvivo will be used to help with management and analysis of data.

#### Quantitative data:

Descriptive statistics will be generated for the baseline characteristics of the study participants, and frequencies and percentages will be presented for categorical variables while mean and standard deviation will be presented for continuous variables.

To assess effectiveness of gout action plan, the continuous outcome between the two groups will be compared using independent t-test. When outcomes are categorized into binary outcomes, Chi-square test will be performed. The baseline outcomes will also be assessed with demographic using either Chi-square test or Fisher's Exact test for categorical variables, and independent t-test or ANOVA for continuous variables to ensure both groups are comparable. Multivariate linear regression model will be performed with each outcome below and the following covariates to determine effectiveness of the intervention: intervention (gout action plan), baseline outcome and any demographic factors with a p-value of less than 0.1 in the bivariate analysis. All analyses will be performed using SPSS software version 29.0. A p-value of less than 0.05 is considered to be statistically significant.

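### One measured outcome can be tested three ways at p<0.05 with no main analysis named, and linear regression is the only adjusted model, even for a binary outcome

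*Protocol*

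**What the plan says.** Protocol section 8.2 (Quantitative data) gives three routes for comparing the arms:

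- an independent t-test for continuous outcomes, without baseline adjustment;
- a chi-square test for categorised ones: "When outcomes are categorized into binary outcomes, Chi-square test will be performed";
- an adjusted model: "Multivariate linear regression model will be performed with each outcome below". Its covariates are the intervention, the baseline value and any demographic factor that passes a 0.1 screen.

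One threshold applies throughout: "A p-value of less than 0.05 is considered to be statistically significant".

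The section does not say which route carries the conclusion, or whether a categorised version replaces the continuous one or is added to it. No list of outcomes follows the regression sentence. Section 5 names them as gout flares, uric acid and quality of life, with quality of life measured by EQ-5D-5L. No adjusted model other than linear regression is given.

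**The concern.** Uric acid is a laboratory value and EQ-5D-5L a scored questionnaire, so neither has to be categorised before it is compared. As written, either can be tested as measured, tested again after a split, and tested a third time with adjustment. A reader who sees one p-value below 0.05 among the three cannot tell what error rate stands behind it.

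Two further consequences follow. If the binary result is the one reported, precision is lost in a trial that expects about 25 analysed patients per arm. If the binary version is adjusted, the only model on offer is linear, which does not match a 0/1 outcome and can give fitted values outside 0 to 1. An analysis plan that followed this text faithfully would carry both problems forward.

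**Working it through.** **Inputs from the protocol.** Significance level 0.05 (section 8.2; two-sided assumed, since 8.2 does not say). Allocation is 1:1 and follow-up 24 weeks (section 5, Randomization). Pilot size (section 8.1): "pilot trial sample size to be 25 per treatment arm for small effect size of 0.2 for a main trial designed with 90% power", then "assuming a potential 30% attrition rate".

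**Inputs assumed.** Normal outcome, no true effect, Pearson chi-square without continuity correction, one cut at the population median, and a correlation of 0.5 between baseline and 24 weeks (range 0.3 to 0.7). The protocol gives no correlation.

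**Step 1. The plan's own sample size.** 25 / (1 − 0.30) = 35.7, rounded up to 36 per arm and 72 in total. This reproduces the stated size. In reverse, 36 × 0.70 = 25.2, so the analysed number lies between about 25 and 36 per arm. Both ends are used below.

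**Step 2. Each test on its own, under no effect (simulated).**

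| Rejection rate | 25 per arm | 36 per arm |
|---|---|---|
| t-test | about 5% | about 5% |
| chi-square, one fixed median cut | 6.5% | 4.4% |
| baseline-adjusted linear model, continuous outcome | about 5% | about 5% |
| linear model on a binary outcome, event rates 10% to 50% | 4.2% to 5.2% | 4.8% to 4.9% |

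No single test is materially off. The 6.5% reflects the discreteness of the chi-square at that size.

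**Step 3. At least one of several significant, under no effect (simulated).**

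| Tests counted | 25 per arm | 36 per arm |
|---|---|---|
| t-test or chi-square | about 8.9% | about 7.2% |
| any of the three, correlation 0.5 | about 11% (10.8%) | 9 to 10% (9.6%) |
| any of the three, correlation 0.3 to 0.7 | 10.2% to 11.9% | 8.5% to 10.4% |

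The three-test rows come from 200,000 simulated trials per setting. The adjusted model there contains treatment and baseline only, so the 0.1 covariate screen in section 8.2 is left out.

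**Step 4. Information lost by a split.** For a normal outcome cut at quantile q, with c the normal quantile, relative efficiency = φ(c)² / [q(1 − q)]. At the median this is 0.3989² / 0.25 = 0.637 = 2/π, a loss of 36%. Then 25 × 0.637 = 15.9, so 25 per arm carry the information of about 16. The median is the most favourable cut: the loss is 42% at the 30th percentile and 66% at the 10th.

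**The case against.** The strongest reply has four parts.

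- **The continuous analyses stay in the plan.** The t-test and the adjusted regression are planned without condition, and nothing says that a binary version replaces them. This stands: the 36% loss arises only where the binary result is used instead.
- **Cut-points belong in the statistical analysis plan.** This also stands, and their absence here is not part of the point. A reader might infer that cut-points will be picked from the data. Keeping the best of 3 to 9 cuts would give 14% to 27% false positives at 25 per arm and 12% to 26% at 36. The protocol plans no such search, so those figures do not describe it.
- **The chi-square and the linear model are sound tests.** Largely true. A split at the sample median rejects 8.9% of the time at exactly 25 per arm, and a reader might take that as proof that dichotomising inflates error. It is discreteness: the same exact calculation gives 4.2% at 24, 5.1% at 26 and 3.3% at 36. Nor does linear regression on a binary outcome inflate error (Step 2). The objection to it is the mismatch of model and outcome.
- **Effectiveness is only preliminary.** It is the second of two secondary aims of a pilot sized by rules of thumb, and a clinically defined binary outcome is legitimate. This lowers the stakes. However, section 8.2 still attaches a significance threshold, and hypothesis 4 in section 2 states that the action plan is effective.

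What the reply does not answer is that three tests of one outcome stand side by side with no order among them.

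**Conclusion.** The point holds in a limited form. Section 8.2 permits three tests of the same measured outcome, each at 0.05, without naming one as the main analysis. Read as any-of-three, the false-positive chance for a single outcome is roughly double the stated level: about 11% at 25 per arm and 9 to 10% at 36. This needs no cut-point search. It rests on a normal outcome, one fixed median cut, two-sided tests and an assumed baseline correlation of 0.5, and it changes little between 0.3 and 0.7. EQ-5D-5L and flare counts are probably not normal, so the figures fit uric acid best.

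The information loss of 36% or more applies only where a binary result stands in for the continuous one. The sample size of 36 per arm reproduces and is unaffected. The documents do not support a claim that linear regression wastes information or inflates error, or that cut-points are to be chosen after the data are seen.

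**What to change.** In section 8.2:

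1. Name the baseline-adjusted linear model already described there (ANCOVA) as the single effectiveness analysis for uric acid and for EQ-5D-5L. Report the adjusted difference with a 95% CI. The unadjusted t-test then no longer serves as a rival test.
2. Drop the parallel chi-square tests of categorised versions of these two outcomes.
3. If a binary version such as uric acid at target is kept, prespecify it as supportive, report a risk difference with a small-sample CI, and use a model suited to binary data, such as logistic regression, if it is adjusted.

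The cost is a few sentences, with no change to patients, visits or sample size. The small downside is losing the freedom to add categorised tests later.
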